Pregnant women will be identified through the COPS² study database if they appear on one or more of the data sources listed for the identification of pregnant women in Table 1.

Table 1: Overview of data sources used for analysis

Data	Data source

Datasets required to identify pregnant women in the general population and associated pregnancy start and end dates:
	
 • New national data return developed as part of the response to the COVID-19 pandemic providing information on women booking for antenatal care with NHS maternity services: for identification of women with ongoing pregnancies in near real-time (all other records that identify end of pregnancy events) • GP consultation data: for identification of women with early miscarriage or ectopic pregnancy not managed in hospitals • Scottish Morbidity Record (SMR) 01: for identification of women with early miscarriage or ectopic pregnancy managed in hospitals • Termination of pregnancy statutory notifications (AAS records) • SMR 02: for identification of later miscarriage, stillbirth, and live births managed in hospital (and some home births) • National Records of Scotland (NRS) statutory stillbirth registrations • National Records of Scotland (NRS) statutory live birth registrations • New national data return developed as part of the response to the COVID-19 pandemic providing information on live births notified by maternity services to NHS Board child health administrative departments: for near real-time access to data that allows intergenerational linkage of records relating to mothers and their babies. 
Note that this is already established as part of the COPS study and methodology is set out in the Protocol for estimating the number of COVID-19 vaccinations delivered to pregnant women in Scotland and for describing the uptake and coverage of vaccination in the pregnant population.

Datasets required to identify characteristics of pregnant population
	
 • Covariates of interest include: Maternal age, deprivation score, urban/rurality score, ethnicity, pre-pregnancy clinical vulnerability exc diabetes, diabetes, BMI, smoking status, and linked PCR test data to capture confirmed cases of COVID-19 infection. 
Note that all are available through the COPS study database.

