
Datasets required to identify vaccinated individuals
	
 • Data from the National Clinical Data Store (NCDS). Information recorded on the National Vaccine Management Tool (VMT) and GPIT system (Primary care practice medical record database) flows to the

² Stock SJ, McAllister D, Vasileiou E, *et al.* COVID-19 in Pregnancy in Scotland (COPS): protocol for an observational study using linked Scottish national data. *BMJ Open* 2020;**10**:e042813. doi: 10.1136/bmjopen-2020-042813. Available from: [COVID-19 in Pregnancy in Scotland \(COPS\): protocol for an observational study using linked Scottish national data | BMJ Open](#)

	NCDS, from where it is cleaned and then linked to the COPS data. Relevant data of interest: vaccination date, type, dose.
Datasets required to identify outcomes of interest	
 Data from a number of sources that hold pregnancy, maternal and neonatal outcome data will be brought into the COPS study dataset. Sources include: SMR01, SMR02, national linked anomaly database, SICSAG critical care admissions, NRS deaths.

3.5: Study Variables

3.5.1: Study Outcomes

Maternal, pregnancy and neonatal outcomes of interest are listed in Table 2. In our main analyses, we will assess the risk of each outcome in vaccinated women and their unvaccinated controls (i.e. classifying each woman as having the outcome or not), and will not attempt to capture any differences between the groups in the time to these events. As noted in Table 2, there are different periods of risk for each outcome (referred to as “outcome-specific follow-up period” throughout this protocol). For example, women will be considered at risk of any miscarriage from conception up to 23⁺⁶ weeks gestation, and at risk for stillbirth from 24⁺⁰ weeks gestation to the end of pregnancy. Women without an observed outcome who had not completed follow-up to the end of the follow-up period for a specific outcome in either the pre-pandemic (i.e. outcome-specific follow-up period not completed before 01 March 2020) or in the pandemic time period (i.e. outcome-specific follow-up period not completed before date of data extraction) will not be eligible for inclusion in the analysis for that outcome.

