For the matched cohort study, the primary comparison for each outcome will be between women vaccinated in the six weeks preceding conception or up to the end of the outcome-specific exposure period within pregnancy and unvaccinated pregnant women from the pre-pandemic period. Only women who had been followed-up to the end of the outcome-specific follow-up period on the 29 February 2020 are eligible to be controls for that outcome analysis. Women who have COVID-19 infection from six weeks preconception up to the end of the outcome-specific follow-up period will

not be eligible for inclusion in the vaccinated group for this primary analysis. Each individual in the pregnant vaccinated cohort will be matched to three individual unvaccinated pregnant controls, if possible⁵. Different pregnancies from a single woman can be matched to different cases, and if a case had a pregnancy in the pre-pandemic period, that pregnancy is a valid control, as long as the woman is not matched to herself. Here the assumption is that pregnancies are independent. A sensitivity analysis will be conducted, removing women who are vaccinated in the six weeks preconception – and her controls – from the analysis.

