With the pre-pandemic period being used as the baseline, there is an assumption that the pandemic has not substantially affected the outcomes of interest through, for example, changes in engagement and provision of maternity services. To investigate this, a supplementary analysis will be conducted with pregnant unvaccinated controls from the pandemic vaccination period (from 08 December 2020 to date of data extraction). In this supplementary analysis, we will exclude women (from both the vaccinated and unvaccinated group) who had any record of COVID-19 infection from six weeks preconception to the end of the outcome-specific follow-up period. However, given that there is potential for vaccination to impact on maternal, pregnancy and neonatal outcomes by changing the risks of acquiring COVID-19 and experiencing severe illness, we will also conduct a second supplementary analysis with pregnant unvaccinated controls from the pandemic. In this, we will retain both vaccinated and unvaccinated women with a confirmed record of COVID-19 infection during pregnancy and preceding the end of the outcome-specific follow-up period. For both these supplementary analyses, women who were vaccinated >6 weeks pre-conception will be included in the control group (as not vaccinated in pregnancy), however sensitivity analyses (if sample size permits) will be conducted to investigate any differences between pairs where the control is completely unvaccinated versus pairs where the control received vaccination >6 weeks pre-conception (e.g. vaccinated pre-‘pregnancy’). Additional supplementary analyses removing women who are vaccinated in the six weeks preconception will be considered for the analyses using women from the pandemic period as controls, if we observe an impact of removing these women in the primary analysis using pre-pandemic controls.

Maternal and gestational age are known to be important risk factors for adverse events in pregnancy (e.g. miscarriage strongly influenced by maternal age). Consequently, the cohorts will be matched by maternal age (± 1 years but relaxed (i.e. possibly $\pm >1$ year) at the tails of maternal age distribution as fewer individuals available for matching), and gestational age (exact match, i.e. same week however allow for relaxation of this at the tails of the gestation distribution).

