Characteristics (e.g. covariates) of the vaccinated and unvaccinated cohorts (from the pre-pandemic and pandemic vaccination time periods), and of the number and risk of all outcome events in the vaccinated and unvaccinated groups will be described to assess the comparability of the groups and to provide better understanding of the data. Summary statistics on the dose, type and class of vaccination in the vaccinated population will be described. Median, range and inter-quartile range of the gestational week of vaccination will be calculated.

Summary statistics and plots of time from vaccination (or matching) to date of outcome will be conducted to provide additional contextual information and to explore plausibility of gaps or clustering of the outcomes in time. As this will not be a time-to event analysis, it will be important to explore descriptively whether there are differences in the temporal trends of the outcomes by vaccination status.

Summary tables of the number and risk of each outcome in the vaccinated and unvaccinated pregnant cohorts, overall, by covariates, and by vaccine type, class, dose number, will be produced.

4.4: Statistical analyses

Maternal, pregnancy and neonatal outcomes in the vaccinated and unvaccinated pregnant cohorts will be compared using conditional logistic regression, where possible. This model type is used to account for matching. Odds ratios (ORs) with 95% confidence intervals will be produced for each comparison and a correction for multiple testing applied (e.g. Benjamini and Hochberg).

The exception will be for pregnancy outcomes where there is a competing risk (i.e. each woman can only have one of these outcomes), such as miscarriage, ectopic pregnancy, termination of pregnancy, stillbirth, and live birth. These will be examined using conditional multinomial logistic regression. The reference for each comparison when examining pregnancy outcomes will be live births (or ongoing pregnancies at a relevant gestation when studying early pregnancy outcomes only). Age, gestational week and season/quarter (when included in the matching strategy) will also be included in the model to account for matching. Termination of pregnancy is not an outcome of interest but it will need to be included in models as a competing risk.

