5.0 Potential limitations

There are a number of limitations that need to be considered when conducting the analysis and interpreting the results. Some of the key limitations are as follows:

1. Lag in data becoming available for women recently captured within the COPS study database:
Due to the way the COPS cohort is derived, there is a lag of up to three months before conceptions are identified and hence the corresponding pregnancies included in the study dataset. This is because either antenatal booking, or an early spontaneous pregnancy loss or termination of pregnancy prior to booking, must occur, and the relevant record be returned to PHS, prior to the pregnancy being identified and the conception retrospectively imputed. These events will usually occur within three months of conception. The COPS cohort is refreshed monthly: more frequent refreshes are not feasible as key source datasets (in particular SMR02) are only updated monthly. This means that, using any month's COPS cohort plus up-to-date vaccination data, will likely fail to identify some recent vaccination events as occurring during early pregnancy. These will be picked up in subsequent months as the COPS cohort is refreshed. This means that initial data outputs must be understood as provisional.
2. Capture of early pregnancy loss:
Women who have early pregnancy loss and do not seek medical advice will not be captured in the COPS dataset.
3. Insufficient sample size for rare outcomes:
For rarer outcomes, there may be insufficient power to assess the association between vaccination status and the outcome using a matched cohort study design. We will still provide descriptive data for these outcomes and, as mentioned in Section 4.5, we will consider different analytical approaches for rare outcomes.
4. Missing data:
For some covariates, there will be missing data, but this is expected to be minimal based on ongoing assessments of data quality.
5. Recording errors:

There may be errors in recording the pregnancy, maternity or neonatal outcomes and the way in which outcomes are recorded may have changed over time.

6. Unmeasured confounding:

There is the potential for unmeasured confounding given the inherent differences between vaccinated and unvaccinated women which might not be accounted for. Specific examples include occupation, specific comorbidities, and wider healthcare seeking behaviours including engagement with antenatal care.

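### The primary miscarriage comparison can admit vaccinated pregnancies on a booking record alone while pre-pandemic controls appear to need an end-of-pregnancy record, which would bias the odds ratio downward

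*Protocol*

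**What the plan says.** **Entry.** Section 3.4 of the protocol includes pregnant women "if they appear on one or more of the data sources listed for the identification of pregnant women in Table 1". The first source in that table is a "New national data return developed as part of the response to the COVID-19 pandemic providing information on women booking for antenatal care", and its stated role is "for identification of women with ongoing pregnancies in near real-time (all other records that identify end of pregnancy events". Section 5.0, item 1, describes entry in the same way: "either antenatal booking, or an early spontaneous pregnancy loss or termination of pregnancy prior to booking, must occur" before a pregnancy is identified.

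**Completeness of follow-up.** Section 3.5.1 excludes "Women without an observed outcome who had not completed follow-up to the end of the follow-up period for a specific outcome". It explains the test by whether the follow-up period closed before 01 March 2020 or before data extraction. For miscarriage, Table 2 ends that period at 23+6 weeks. No recorded end of pregnancy is required.

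**Reference category.** In section 4.4 the comparison group for pregnancy outcomes is "live births (or ongoing pregnancies at a relevant gestation when studying early pregnancy outcomes only".

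**Comparison.** In section 3.6 the primary controls are "unvaccinated pregnant women from the pre-pandemic period", conceived and followed up between January 2015 and February 2020. To examine pandemic effects, "a supplementary analysis will be conducted with pregnant unvaccinated controls from the pandemic vaccination period".

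**The concern.** The two arms of the primary analysis appear to be assembled by different rules. A pre-pandemic pregnancy is known because it ended in a recorded way. A vaccinated pregnancy may be known only because it was booked. If the later loss was never recorded, had not reached the database by extraction, or the woman left Scotland, she stays in the denominator as a non-event. The equivalent pregnancy in 2017 would leave no trace. Matching on maternal age, gestational week and season does not correct this, because the control drawn for a booking-only pregnancy is one with a known end.

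Non-events would then be added to one arm only. The affected estimates are the primary odds ratios for any miscarriage and for first- and second-trimester miscarriage. The bias is towards no harm or apparent protection, which is the unfavourable direction in a safety study. A disagreement with the contemporary-control analyses could also be put down to pandemic effects, since that is the reason section 3.6 gives for running them.

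**Working it through.** **Inputs from the protocol.** Background miscarriage risk 10% to 20% (Table 2). 5,000 vaccinated against 15,000 controls, later 10,000 against 30,000, with a relative risk of 1.2 among the scenarios (section 3.7).

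**Assumptions.** u is the share of the vaccinated denominator known from booking alone and counted as a non-event. It is not in the protocol, so a range is shown. Controls have none. Pregnancies with a recorded end have control risk r and true relative risk RR. The odds ratios are marginal and ignore the matching.

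**The plan's nearest figure.** Table 6 gives 94% power for 10% risk, RR 1.2 and 5,000 vaccinated. A two-sided 5% test of two proportions gives 94.4% with 10% as the vaccinated risk and 10%/1.2 = 8.33% as the control risk. With 10% as the control risk, which is used below, it gives 97.5%.

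**Bias.** Observed vaccinated risk = r × RR × (1 - u), so observed RR = true RR × (1 - u), whatever r is. With no vaccine effect,

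OR = [r(1 - u)/(1 - r(1 - u))] / [r/(1 - r)].

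For r = 10% and u = 5%: (0.095/0.905)/(0.1/0.9) = 0.945. For r = 20%: (0.19/0.81)/(0.2/0.8) = 0.938.

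| u (assumed) | Null OR, r = 10% | Null OR, r = 20% | True RR 1.2 appears as | Power for RR 1.2, r = 10%: 5,000 / 10,000 vaccinated |
|---|---|---|---|---|
| 1% | 0.989 | 0.988 | 1.188 | 95.9% / 99.9% |
| 2% | 0.978 | 0.975 | 1.176 | 93.5% / 99.8% |
| 5% | 0.945 | 0.938 | 1.140 | 79.7% / 97.5% |

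**Scale against sampling error.** At r = 10% with 5,000 against 15,000, SE(log OR) = √(1/500 + 1/4,500 + 1/1,500 + 1/13,500) = 0.054. The bias is about 0.2 SE at u = 1%, 0.4 SE at 2% and 1.0 SE at 5%.

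**False protection.** With no vaccine effect and r = 10%, a significantly protective result should occur 2.5% of the time. At u = 1% it occurs 3.9% of the time (5,000 vaccinated) or 4.7% (10,000); at u = 5%, 17% or 30%.

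**What can be hidden.** At u = 5% and r = 10%, the observed OR is 1.00 when the true vaccinated risk is 0.10/0.95 = 10.53%, a true OR of (0.1053/0.8947)/(0.1/0.9) = 1.06. To bring RR 1.2 down to 1.00 needs u = 1 - 1/1.2 = 16.7%.

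**The case against.** Several links are inferred. The protocol calls the return new but gives no start date and does not say whether earlier bookings were loaded. Appendix 1 shows that SMR02 also holds antenatal admissions, although Table 1 lists SMR02 only for pregnancy ends. Nothing states outright that a booked pregnancy with no further record is kept as event-free; the wording on completed follow-up could be read to exclude it, and ongoing pregnancies need not include those lost to follow-up. Table 1 refers to a separate protocol for the method of identifying pregnancies. That document is not at hand and may settle the matter. These points stand, and they make the finding conditional. They do not remove it, because this protocol sets a cross-era primary comparison and nowhere requires a recorded end or a common capture rule.

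u may also be small. A booked woman is already in contact with maternity services, and a later loss must escape every source in Table 1. At 1% to 2% the bias is a fraction of a standard error. This stands too, and it limits the size of the claim.

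Finally, supplementary analyses 1 and 2 draw both arms from the same period and sources, and section 5.0, item 5, accepts that recording may have changed over time. The supplementary analyses do avoid the difference between eras. That does not make u equal between their arms: a woman who leaves Scotland after booking but before vaccination can only be an unvaccinated control. Nor do the limitations mention that the route of entry differs by era.

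**Conclusion.** The concern holds in conditional form. If the booking return covers only pandemic-era pregnancies, and booking-only pregnancies are kept as non-events, the primary miscarriage odds ratios are biased downward by a factor of about (1 - u). The direction is certain under those two conditions. The size is not known: a null odds ratio becomes about 0.99, 0.98 and 0.94 to 0.95 at assumed shares of 1%, 2% and 5%.

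A reader might infer that the design masks a miscarriage excess. The protocol does not support that. Small shares attenuate an excess, and only a small one (a true OR of about 1.06 at u = 5%) would vanish. Fully hiding RR 1.2 needs about 17%, and nothing in the protocol suggests a share that large. Nor can it be stated as fact that the return holds no pre-pandemic bookings, or that the investigators have chosen to count women without a recorded end as event-free. Both are readings of the text that the protocol leaves open.

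**What to change.** For the primary miscarriage analyses with pre-pandemic controls (any, first and second trimester), apply one capture rule to both eras:

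- Require a recorded end of pregnancy. Live births known so far only from the new live-birth return can count, since these are also registered with NRS.
- Restrict to conception cohorts old enough to have delivered, with records returned, by extraction. Without this the rule would favour early losses, whose end records arrive before those of deliveries.
- Use recorded later outcomes as the reference in place of ongoing pregnancies.
- State the period that the booking return covers, and report by arm the number of pregnancies known from booking alone, so that u can be seen.

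If earlier reporting is needed, keep the present analysis as provisional and run the restricted version alongside it. Booking-identified ongoing pregnancies can stay in the contemporary-control analyses.

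The change is a filter in data preparation plus one reported count. Its real cost is time: the most recent vaccinated conceptions enter the primary miscarriage analysis some months later, which matters for safety monitoring and is the reason to keep a provisional version.
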